10.1 Flow Diagram and Procedures Table

[figure not shown]

Figure 2. Study Flow Chart

Table 1. Schedule of Study Procedures

Activity	Visit 1 Enrollment/Baseline/ Randomization	Phone Calls Week 1 and Week 6 ± 3 days*	Visit 2 Week 12 ± 7 days Follow-up*
Informed Consent	X		
Demographics and medical history	X		
Modified physical exam	X		
Vital signs	X		X
Inclusion/exclusion criteria	X		
PaO ₂ at rest	X		X
Randomization	X		
ActiGraph and oxygen usage diary distribution	X		
POC distribution [^]	X		
Device training	X	X	
ActiGraph set-up and initialization	X		
ActiGraph data download			X
Usage diary collected			X
St. George's Respiratory Questionnaire	X		X
HADS	X		X
6MWT	X		X
Concomitant meds [†]	X	X	X
Adverse events	X	X	X
Return all study devices ^{**}			X

*After Visit #1

[^] for patients assigned to the POC arm

[†] Respiratory condition-related medications only

^{**} Patients will have the option to purchase their POC device used in the study

10.2 Screening

Trained site study personnel will screen patients for study participation by two methods:

- 1) review COPD patient medical records for existing LTOT users who appear to meet study criteria to approach them about their interest in study participation;
- 2) Ask COPD patients who are prescribed LTOT for the first time during the study enrollment phase and who appear to meet study criteria about their interest in study participation.

10.3 Visit 1: Randomization and Baseline Visit

After a potential study patient has 1) completed the initial informed consent process and signed the study-specific informed consent form, 2) successfully completed the baseline 6MWT, and 3) been determined to meet all inclusion criteria and none of the exclusion criteria, the patient will be randomized in a 1:1 ratio to either SOC long-term oxygen therapy only (control arm) or SOC long-term oxygen therapy plus a POC (treatment arm). Randomization will be stratified by site and will be implemented via small permuted blocks. Randomization assignments will be assigned through the electronic study database and will be obtained by trained site personnel. A patient is considered enrolled at the time of randomization. Patients will be given all study devices relevant to their study arm assignment and will receive training on all devices at the baseline visit. Patients will be instructed to contact their site study staff with any questions pertaining to the study.

10.3.1 Baseline Data Collection

The following information will be collected at baseline:

- Inclusion and exclusion criteria confirmation
- Demographics
- Medical history
- Modified physical exam
- Vital signs (temperature, pulse, respiratory rate, and blood pressure)
- PaO₂ at rest
- SGRQ questionnaire
- HADS questionnaire
- 6MWT results
- Concomitant medications*
- Adverse events
- Protocol deviations

*Respiratory condition-related medications only

10.3.2 Distribution of Study Devices

During the baseline visit, all patients will receive the following devices:

- ActiGraph activity monitor

In addition to the above devices, treatment arm patients will also receive one POC device.

Patients will be trained on the use of all study-related devices during the baseline visit and will be provided with the associated device instructions/guides for reference. All patients will be instructed to complete oxygen use diaries each day.

10.3.3 Initializing the ActiGraph GT9X Device

The following components of the ActiGraph GT9X device will be used for this study. Items in **bold** will be distributed and explained to the patient by a trained research team member.

- **ActiGraph Link**
- **Link Wrist Band**
- **Single Dock**
- **CentrePoint (CP) Data Hub**
- USB Cables
- AC Wall Plug

A trained member of the study team will install the ActiSync software on a designated computer in advance of enrolling the first study patient. Study personnel will be emailed invitations to the CentrePoint platform. The battery for each patient's ActiGraph device will be fully charged (for approximately three hours) in anticipation of enrollment. The ActiGraph device will be programmed using applicable instructions found in the ActiGraph GT9X Link + CentrePoint Quick Start Guide and/or the ActiGraph Site User Guide (in the eTMF) during the baseline visit. Additional ActiGraph GT9X device programming and use instructions will be provided during the Site Initiation Visit.

10.4 Study Phone Calls

A trained member of the site research team will call patients at 1 week (± 3 days) and 6 weeks (± 3 days) after study enrollment. The purposes of the phone calls are to:

- Assess for previously unreported adverse events
- Obtain updates on any ongoing adverse events
- Obtain any updates on respiratory condition-related concomitant medications
- Assess patient protocol compliance, i.e., use of ActiGraph devices, oxygen usage diaries, POC usage (if randomized to the treatment arm)
- Answer any study-related questions the patient may have
- Address any study-related concerns the patient may have
- Provide additional study device training and support as needed

Phone calls will be documented on a standardized study worksheet for source documentation.

10.5 Visit 2: 12-Weeks Post Randomization

Patients will return all study devices at the 12-week visit and will continue with their prescribed COPD care plan, including LTOT. Patients will have the option to purchase their POC device used in the study.

10.5.1 Visit 2 Data Collection

The following information will be collected 12 weeks ± 7 days post-randomization:

- Vital signs
- PaO₂ at rest
- SGRQ questionnaire
- HADS questionnaire
- 6MWT results
- Oxygen usage diary
- Concomitant medications
- Adverse events
- Protocol deviations

10.5.2 Data Management for the ActiGraph GT9X Device

A trained member of the study team will plug the device into the designated computer at the 12-week visit by following the instructions in the ActiGraph GT9X Link + CentrePoint Quick Start Guide and/or the ActiGraph Site User Guide (in the eTMF). The data will be automatically uploaded to the CentrePoint platform.

Additional data download instructions may be provided during study initiation and/or throughout the study as necessary. After data have been uploaded from the ActiGraph device, a trained study team member who uploaded the data should submit the data for data management and analysis as instructed in study training materials.

11 Concomitant Medications

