Study Population	Patients diagnosed with COPD who are prescribed to receive continuous (24/7) long-term oxygen therapy.
Study Design	This is a post-approval, randomized, unblinded, multicenter, parallel group design study with patients randomized to either control (SOC long-term oxygen therapy [SOC arm]) or active treatment (SOC long-term oxygen therapy plus a POC [POC arm]) in a 1:1 ratio. All patients will be provided with an activity monitor to wear continuously to monitor physical activity, and a usage diary to collect oxygen usage. Eligible patients have COPD and are prescribed to receive long-term oxygen therapy. At the enrollment/baseline visit, patients will be consented, randomized, receive their study devices with training (activity monitor, oxygen use diaries, and an assigned POC if randomized to the POC arm), and complete the Visit 1 assessments. At Weeks 1 and 6 after the enrollment/baseline visit, they will receive a phone call from the site to reinforce training on study devices, oxygen usage and study requirements, and adverse event assessment. At the 12-week follow-up/final visit, they will complete an in-clinic visit to return all study devices (POC, activity monitor and oxygen use diaries); have activity monitor device data downloaded by the site; and complete the 12-week assessments. Assessments include a 6MWT, St. George's Respiratory Questionnaire and HADS. Data from the activity monitor will be used to document changes from baseline through 12-week physical activity measures for primary endpoint analysis. Patients will be assessed for adverse events at each encounter after signing the ICF. Study participation is complete when the 12-week follow-up visit is completed. Data from the ActiGraph device will be uploaded by the study sites for compliance assessment and statistical analyses.
Study Centers	Up to 20 centers in the United States will participate in this study.

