3.2.3 ActiGraph GT9X Link

All subjects enrolled in the study will receive an ActiGraph GT9X Link wearable device to collect physical activity data throughout the study. A CentrePoint (CP) data hub is also included with the ActiGraph device to upload the physical activity data.

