11.1 Analysis Sets

11.1.1 Intention-to-Treat

The intention-to-treat analysis set (ITT) consists of randomized subjects who begin long-term oxygen therapy, with or without a POC, receive an ActiGraph device, and have at least baseline ActiGraph data. The ITT analysis set will be used as the primary analysis set in analyzing all endpoints.

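### The plan schedules one ActiGraph download, at Visit 2, and does not say whether the home hub transmits, so an unrecovered monitor may cost a patient's place in the SAP's ITT set

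*Protocol*

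**What the plan says.** **Retrieval.** Table 1 (Protocol 10.1) has one row for "ActiGraph data download", marked under Visit 2 only. Protocol 10.5.2 describes that step: "A trained member of the study team will plug the device into the designated computer at the 12-week visit". The synopsis gives sites the upload and ties compliance assessment to it: "Data from the ActiGraph device will be uploaded by the study sites for compliance assessment and statistical analyses".

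**Home hub.** Protocol 10.3.3 lists the "CentrePoint (CP) Data Hub" among the items that "will be distributed and explained to the patient by a trained research team member". SAP 3.2.3 gives its purpose: "A CentrePoint (CP) data hub is also included with the ActiGraph device to upload the physical activity data". Neither document states a transmission schedule, a check that data have arrived, or whether hub data enter the analysis. Protocol 10.5.2 leaves room for further download instructions, and 10.3.3 and 10.5.2 refer to user guides held in the eTMF.

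**Calls.** At Weeks 1 and 6 (each ±3 days) sites are to "Assess patient protocol compliance, i.e., use of ActiGraph devices, oxygen usage diaries" and POC use (Protocol 10.4). The source of the compliance information is not stated.

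**Early leavers.** Protocol 12.2 asks for an in-person final visit with return of devices. Protocol 16.4 requires return at Visit 2 or at earlier termination. Neither names a download at an early visit.

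**Analysis sets.** SAP 11.1.1 requires, among other things, that ITT subjects "have at least baseline ActiGraph data", and makes that set primary for all endpoints. Protocol 14.4 defines ITT as all randomised patients and bases the safety evaluation on it. SAP Section 6 limits the primary analysis to subjects with PAL at both baseline and week 12.

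**The concern.** Baseline PAL is measured in the first week after the monitor is issued, not before randomisation. Unless the hub sends them, those data stay on the monitor until a site docks it, on the written schedule about eleven weeks later. Whether a patient has baseline data then depends on recovering the device, which is an event after randomisation.

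The SAP makes baseline ActiGraph data a condition of ITT membership for every endpoint. A death after which the monitor is not recovered could therefore drop out of the mortality analysis, and a hospitalised patient later lost to follow-up could drop out of the hospitalisation analysis. Exclusion of that kind may be related to the outcome. A patient whose monitor is lost or fails but who attends Visit 2 would lose SGRQ, HADS and 6MWT results already in hand.

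For the primary endpoint the stake is smaller: a failed device or non-wear that nobody sees before week 12, and recorded days that the SAP 11.5 imputations cannot use because they were never retrieved.

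**Working it through.** **1. The plan's own figures.** Inputs from Protocol 14.2: difference 0.1, SD 0.22, two-sided 5%, 80% power, 20% attrition.

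- n per arm = 2 × (1.960 + 0.842)² × 0.22² / 0.1² ≈ 76 by the normal approximation.
- By the noncentral t, power is 0.795 at 76 and 0.800 at 77 per arm, so the plan's 77 is reproduced.
- SAP 3.1 plans 95 per arm. Early leavers at 20%: 0.20 × 95 = 19 per arm.

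**2. What each kind of loss does under the SAP rules.**

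| Case | Hub transmits | Hub does not transmit |
|---|---|---|
| Early withdrawal, monitor returned and docked | In ITT; no week 12 PAL | Same |
| Death or loss to follow-up, monitor not recovered | In ITT; no week 12 PAL, but weeks 7-12 may feed SAP 11.5 | No baseline; out of ITT for every endpoint |
| Patient attends Visit 2, monitor lost or failed | In ITT; data kept up to the last upload; failure can be seen | No baseline; out of ITT despite other Visit 2 data |
| Monitor returned, week 12 not worn | In ITT; non-wear could be seen earlier | In ITT; non-wear found only at download |

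The ITT consequence arises only in the second and third rows, and only in the right-hand column.

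**3. How many.** Let r be the share of early leavers whose monitor is never recovered. The documents do not give r, so these values are assumptions, and the hub is taken to have sent nothing.

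| r | Per arm of 95 (19 × r) | Share of arm | Of 109 enrolled (0.20 × 109 = 21.8, × r) |
|---|---|---|---|
| 0 | 0 | 0% | 0 |
| 0.25 | 4.75, about 5 | 5% | about 5 |
| 0.50 | 9.5, about 10 | 10% | about 11 |
| 0.75 | 14.25, about 14 | 15% | about 16 |

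**4. Primary comparison.** An early leaver has no week 12 PAL, so recovering week 1 restores ITT membership but no primary power. For scale only, power (noncentral t, 0.1, SD 0.22) by the total share lacking primary data for any reason:

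| Share lost | 190 enrolled | 109 enrolled |
|---|---|---|
| 0% | 0.876 | 0.652 |
| 5% | 0.859 | 0.630 |
| 10% | 0.840 | 0.606 |
| 15% | 0.819 | 0.581 |
| 20% | 0.795 | 0.555 |

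Each further 5 points of loss costs about 2 to 3 points of power. Only losses among patients still in the study (device failure, non-wear) can be reduced by earlier checks.

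**5. Timing of the existing contacts.** The Week 1 call falls on day 7 ± 3, so days 4 to 10, and can come before the baseline week ends. The Week 6 call falls on day 42 ± 3, so days 39 to 45. The SAP 11.5 windows are weeks 7-12 and 10-12. The two calls alone therefore cannot secure the imputation data; uploads have to continue through the study.

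**The case against.** The strongest reply is that the documents do not exclude home upload. The hub is explained to the patient, its stated purpose is to upload, site staff are invited to the CentrePoint platform, and the operating detail sits in guides that are not part of these documents. Week 1 may well be on the platform long before a monitor goes missing. This stands. A reader might infer that an unreturned monitor always loses the baseline week, but the documents support that only if the hub does not transmit. What remains is that the written plan neither requires nor checks the one route that would protect the data.

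Two other tempting readings also go too far. One is that the calls rely on patients' own reports of monitor use: Protocol 10.4 does not say how compliance is judged. The other is that every early withdrawal loses data: Protocol 12.2 and 16.4 call for the device back, and compensation depends on its return (17.4). The gap there is narrower, namely that no download is named at that visit. These provisions do not cover death, loss to follow-up, or a lost or failed device.

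It can also be said that the serious consequence comes from the SAP's ITT rule, not from the download schedule. That is right. Under the Protocol 14.4 definition a lost monitor would remove nobody from mortality or hospitalisation, so the fix has to address the definition too.

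**Conclusion.** The point holds in conditional form. One site download is scheduled, at Visit 2; the hub's role is unstated; and no check of uploaded data before week 12 is written down. If the hub does not transmit, an unrecovered monitor loses all activity data and, through SAP 11.1.1, the patient's place in every endpoint analysis. This conflicts with the protocol's all-randomised set.

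The illustrative size is 5% to 15% of each arm. It rests on the plan's 20% attrition, an assumed 25% to 75% non-recovery among early leavers, and no hub transmission. It is zero if the hub sends week 1 or all monitors come back. The main harm is to event endpoints. It should not be read as a loss of primary power from early leavers, who lack week 12 PAL in any case. For PAL the harm is limited to device failure or non-wear not seen in time, and to unretrieved days that SAP 11.5 could have used. This is an inexpensive improvement to the plan, not a fault that invalidates the primary analysis.

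**What to change.** **Protocol Table 1, 10.4 and 10.5.2**

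- Schedule hub upload throughout the study and keep docking at Visit 2 as back-up.
- Confirm on CentrePoint that the baseline week has arrived once day 7 has passed: at the Week 1 call, or by a remote check soon after if the call falls earlier. This secures week 1 data but cannot repair non-wear in that week.
- Review uploaded wear data at the Week 6 call.
- When Visit 2 is being scheduled, and before week 12 begins, check wear and remind the patient.
- Name a download at the early-termination visit, alongside the device return in 12.2 and 16.4.

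**SAP 11.1.1**

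- Reconcile the ITT set with the all-randomised definition in Protocol 14.4, so that missing ActiGraph data do not remove patients from mortality, hospitalisation and other non-ActiGraph endpoints. The PAL analysis keeps its own data requirement in Section 6.

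**Cost.** The hub, the platform and both calls are already in the plan. The changes are a row in Table 1, lines on the call worksheet, one remote check, a revised definition, and a few minutes of site time per check. The SAP (Section 2) records that the study closed early at 109 enrolled, so the collection changes bear on the protocol as a design. The ITT definition can still be settled in the analysis, and the report can state how many monitors were not recovered and whether hub data existed for them.

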11.1 Medications

Only respiratory condition-related concomitant medications taken at baseline and during the study, including changes, will be recorded on the Concomitant Medication eCRF. There are no prohibited medications for this study.

12 Patient Completion and Withdrawal

12.1 Patient Completion

A patient's participation in this study is considered complete after the 12-week follow-up visit is completed.

12.2 Patient Withdrawal

A patient may withdraw (or be withdrawn) from the study prematurely for the following reasons:

- Withdrawal of consent by patient
- Withdrawal of patient by investigator
- Lost to follow-up
- Termination of study by the sponsor
- Death
- Other (to be specified).

The reason for termination will be recorded on the appropriate eCRF. In the event that a patient withdraws from the study, a final study visit should be conducted in person. At a minimum, the patient will return all study-related devices and accessories during the final study visit. If the patient wishes to purchase their study POC, they may do so upon study withdrawal. Other final study-related activities (e.g. questionnaire completion) may be conducted at the investigator's discretion and with the patient's agreement.

12.3 Screen Failures

Screen failures are those patients who have signed the informed consent but are then determined to be ineligible for randomization to a study arm. A log of all study screen failures will be maintained by each investigational site. The reason(s) for screening failure will be recorded on the log.

13 Adverse Events

13.1 Definitions

13.1.1 Adverse Event

For the purposes of this study, an adverse event (AE) is defined as any undesirable/unusual medical experience that occurs to a patient during the study, whether or not it is considered to be device related, including (but not limited to) those events that result from the use as stipulated in the protocol. If an investigator is unsure about whether to report a finding as an adverse event, s/he should report the event on the AE eCRF.

13.1.2 Serious Adverse Event

A serious adverse event is an adverse event that:

- Leads to death, or
- Leads to serious deterioration in the health of a patient that:
 - results in a life-threatening illness or injury,
 - results in permanent impairment of a body structure or body function,
 - requires inpatient hospitalization \geq 24 hours or prolongation of existing hospitalization,

- results in medical or surgical intervention to prevent permanent impairment to a body structure or a body function.

13.1.3 Anticipated Adverse Events

Warnings, contraindications, and hazards are outlined in the User/Operator Manual for the POCs and should be reviewed with patients when they receive their study device(s). All study devices are to be used in accordance with their respective approved, current instructions found in the manual. Anticipated adverse events include events that are reasonably expected to occur as a result of the patient's disease state or treatment.

COPD-related Anticipated Adverse Events:

- COPD exacerbation and related symptoms including:
 - Cough
 - Dyspnea (shortness of breath)
 - Excessive mucus production
 - Wheezing
 - Chest tightness
 - Cyanosis
 - Respiratory infections
 - Headache
 - Fever
 - Confusion
 - Chest pain
- Lack of energy (fatigue)
- Unintended weight loss
- Swelling in ankles, feet, or legs
- Death

LTOT-related Anticipated Events:

Anticipated adverse events associated with LTOT include, but are not limited to, the following:

- Fires
- Burns
- Nosebleed
- Dry mouth
- Dry throat
- Headache
- Tripping/falling over equipment
- Electrical shock and damage
- Noise irritation
- Low oxygen level due to improper equipment use, improper accessory use, or device malfunction

13.2 Adverse Event Assessment and Reporting

13.2.1 Adverse Event Assessment

Adverse event information will be collected on all patients. At every patient encounter throughout the study, the investigator will inquire about adverse events since the last encounter. Patient medical records

will be reviewed throughout the study and at study completion to specifically look for AEs and AE updates. Study staff will ask specific questions during the 1- and 6-week phone calls to assess for AEs.

13.2.2 Adverse Event Reporting

Adverse events (AEs) are to be reported in the electronic study database on an AE eCRF as soon as possible after discovery by the site and are to be updated with new information and upon final resolution of the event. Supporting source documents for SAEs may be requested by RCRI; if requested, these documents are to be de-identified, labeled with the patient's study ID number, and promptly provided via email to RCRI or uploaded to the electronic study database. Adverse events will be evaluated by the investigator and classified for seriousness (as defined in Section 13.1.2), relatedness, and severity:

Relatedness

Adverse events will be judged by the Investigator as to their relatedness to the study device or procedure using the following classifications:

- Unrelated: The event is due to the underlying disease state or concomitant medication or therapy not related to the study-specific devices or procedures.
- Probably Not Related: The event had no significant temporal relationship to the study-specific devices or procedures and/or a more likely alternative etiology exists.
- Possibly Related: The event had a strong temporal relationship to the study-specific devices or procedures and alternative etiology is equally or less likely compared to the potential relationship to the study-specific devices or procedures.
- Probably Related: The event had a strong temporal relationship to the study-specific devices or procedures and another etiology is unlikely.
- Unknown: Relationship of the event to the study-specific devices or procedures and alternative etiology is unknown.

Severity

Adverse events will be categorized by the Investigator as mild, moderate, or severe, depending on the event's impact on the subject's daily activity level:

- Mild: Usually transient, requiring no special treatment; does not interfere with the subject's daily activities.
- Moderate: Low-level inconvenience or concern to the subject; may interfere with daily activities, usually resolved by simple therapeutic non-interventional methods.
- Severe: Interruption in subject's daily activity requiring systemic drug therapy or other treatment.

